## 7.5. Multiplicity Considerations

This is a Phase 2b study in which there are two dose levels being compared to placebo, and there are two efficacy endpoints being assessed.

- All hypothesis tests will be 2-sided, performed at the 5% level of significance.
- The primary endpoint needs to achieve a significance level of 0.05 within a Intepirdine dose to proceed to testing the secondary endpoints and therefore maintain an overall 5% significance level for that dose. The two secondary endpoints are tested simultaneously at the 5% significance level.

The primary comparisons of interest are the individual Intepirdine arms vs placebo pairwise tests. The doses will be assessed in a hierarchy, with the 70 mg dose (vs placebo) assessed first. If significant on the primary endpoint ( $p\text{-value} \leq 0.05$ ), then the 35 mg dose (vs placebo) will be assessed. Otherwise, the 35 mg dose will not be assessed.

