## 6. SAMPLE SIZE CONSIDERATIONS

The sample size is based on assumptions of treatment benefit for one primary endpoint, the UPDRS- III total score. A sample size of 70 subjects per treatment group will allow a treatment difference of 4 points between placebo and active treatment in the change from baseline in UPDRS- III score to be detected with 88% power and a 0.05 significance level assuming an underlying standard deviation (SD) of 7.5

There are two secondary endpoints:

- ADAS-Cog 11 total score. A sample size of 80 subjects per treatment group will allow a treatment difference of 3 points between placebo and active treatment in the change from baseline in ADAS-Cog-11 score to be detected with 88% power and a 0.05 significance level assuming an underlying standard deviation (SD) of 6. Under the assumptions of a 2.5, 2.0 and 1.5 point treatment effect, the power is 74%, 55% and 35%, respectively.
- CIBIC+. A sample size of 80 subjects per treatment group will allow a treatment difference of 0.5 points between placebo and active treatment in the observed values in the CIBIC+ to be detected with 91% power and a 0.05 significance level assuming an underlying standard deviation (SD) of 0.95. Under the assumptions of a 0.4 and 0.3 point treatment effect, the power is 75% and 51%, respectively.

Randomization will be stratified according to Baseline MMSE score in the groupings of 14-17 points, 18-21 points and 22-26 points and according to whether subjects are or are not taking a cholinesterase inhibitor as a concomitant medication.

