#### 9.4.1. Secondary Efficacy Endpoint Analyses

The secondary efficacy analyses endpoints are the change from baseline in the ADAS-Cog 11 score at Week 24, and the observed scores of the CIBIC+ at Week 24.

This will be analyzed using similar MMRM methods as the primary endpoint (however, for the CIBIC+, no baseline value or interaction with visit will be included). A Wilcoxon Rank test will also be performed, as will the sensitivity analysis for LOCF to Week 24 and multiple imputation. The sensitivity analyses as being performed on the primary endpoint (CDF, LOCF, and multiple imputation) will be performed for the secondary endpoints.

For the CIBIC+, The number and percentage of subjects in each category of CIBIC+ will also be summarized by visit for each treatment group and tested using a CMH RMS test.

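### SAP 7.5 claims an overall 5% level per dose, but two ungraded secondaries at the full 5% each can take it to 9.75%

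*SAP*

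**What the plan says.** SAP 7.5 sets the rule for every test: "All hypothesis tests will be 2-sided, performed at the 5% level of significance". Within a dose, "The primary endpoint needs to achieve a significance level of 0.05 within a Intepirdine dose to proceed to testing the secondary endpoints", and the SAP draws the consequence that this will "therefore maintain an overall 5% significance level for that dose". The next sentence reads "The two secondary endpoints are tested simultaneously at the 5% significance level".

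The section opens by saying that "there are two efficacy endpoints being assessed". SAP 6 describes UPDRS-III as the one primary endpoint and then says "There are two secondary endpoints", namely ADAS-Cog 11 and CIBIC+. SAP 9.4.1 names the same two. Three endpoints are therefore tested within a dose.

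Across doses, "The doses will be assessed in a hierarchy, with the 70 mg dose (vs placebo) assessed first"; 35 mg is assessed only if 70 mg succeeds on the primary endpoint.

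Protocol 10.1 and SAP 7 repeat the gate and add no adjustment. The Statistical Methods entry in the protocol summary also asserts a 5% level within a dose, but refers to a single secondary endpoint.

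**The concern.** A gate followed by one secondary test at 5% does keep the level at 5% for a dose. A gate followed by two unadjusted tests at 5% does not. Once UPDRS-III is a true positive, the gate gives no further protection, and the secondaries form a family of two tests at full level. No order, alpha split, step-down rule or requirement that both succeed is given in either document.

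The claim fails in the situation the trial hopes to be in, where a dose has a real motor benefit. A lone result at p ≤ 0.05 on cognition or global function would then be reported as controlled at 5% for that dose when it is not.

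**Working it through.** **Inputs.** Two-sided 0.05 for every test, the gate and the two secondaries come from SAP 7.5. SAP 6 gives UPDRS-III as 70 per group, 4 points, SD 7.5, power 88%; ADAS-Cog 11 as 80 per group, 3 points, SD 6; and CIBIC+ as 80 per group, 0.5 points, SD 0.95. Correlations between the test statistics are not given. They are assumed here, from 0 to 0.7.

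**Step 1: where the stated 5% holds.** If the dose has no effect on UPDRS-III, any false claim first requires a false rejection on UPDRS-III, so the rate is at most 5%. If UPDRS-III and one secondary are truly affected, only one true null remains, tested at 5%, and the rate is again at most 5%. The problem is confined to a real UPDRS-III effect with both secondaries null.

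**Step 2: power of the gate.** The noncentrality is 4 / (7.5 × √(2/70)) = 3.155. Power is about Φ(3.155 - 1.960) = Φ(1.195) = 88.4% by the normal approximation and 88.0% by the noncentral t. The SAP's 88% is reproduced.

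**Step 3: gate certain to open.** With independent secondaries the rate is 1 - (1 - 0.05)² = 1 - 0.9025 = 9.75%. With correlation r it is P(|Z₂| > 1.96 or |Z₃| > 1.96) under a bivariate normal distribution.

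**Step 4: gate at the planned 88%.** If UPDRS-III is uncorrelated with the secondaries, multiply Step 3 by 0.88; at r = 0 this is 0.88 × 9.75% = 8.58%. If all three endpoints share correlation r, use a trivariate normal with UPDRS-III mean 1.960 + 1.175 = 3.135 and the secondaries at 0.

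Chance of at least one false secondary rejection for a dose (computed before rounding):

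| Correlation r | Gate certain | 88% gate, UPDRS-III uncorrelated | 88% gate, all three share r |
|---|---|---|---|
| 0 | 9.75% | 8.58% | 8.58% |
| 0.3 | 9.51% | 8.37% | 7.95% |
| 0.5 | 9.07% | 7.99% | 6.90% |
| 0.7 | 8.35% | 7.34% | 5.44% |

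Using 3.155 in place of 3.135 moves the 88% columns by less than 0.1 percentage point.

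**Step 5: the same case under Holm.** At least one false rejection requires the smaller p-value to be ≤ 0.025. With the gate certain to open and independent secondaries this is 1 - 0.975² = 4.94%, falling to 4.3% at r = 0.7. Together with Step 1, the level for a dose is then at most 5% in every configuration.

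**The case against.** - **9.75% is a ceiling.** It needs a near-certain gate, no effect on either secondary and uncorrelated secondaries. This is right. At the planned power, 7% to 8.6% covers most of the plausible cases. With an 88% gate and one common correlation, the rate falls below 5% once that correlation exceeds about 0.75. That would be extreme across motor, cognitive and global scales, and a claim to maintain 5% must hold without relying on it.
- **The rates count both directions.** A false finding of benefit has a probability of at most 4.94% with the gate open, and 4.2% to 4.6% at planned power over common correlations 0 to 0.7. This is a fair clarification. The matching one-directional level is 2.5%, so the inflation remains, and the SAP's own 5% is two-sided.
- **Simultaneous testing at 5% could mean a joint 5% for the pair.** No joint procedure is named, and the preceding bullet sets every test at 5%. If joint control was intended, the method still has to be stated.
- **Phase 2b secondaries need no adjustment.** That is a legitimate choice, but the SAP cannot make it and also assert 5% control.
- **The dose hierarchy.** It is sound for the two primary tests, but it does not act on the secondaries within a dose; 70 mg alone shows the problem.

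**Conclusion.** The concern holds. The 5% statement in SAP 7.5 is incorrect as written. When a dose truly affects UPDRS-III but neither secondary, the error rate for that dose is up to 9.75%, and 5.4% to 8.6% at the planned 88% power over the correlations examined. These figures assume normal test statistics and correlations of 0 to 0.7, none of which the documents supply. The primary test is untouched, and the SAP makes no study-wide claim across doses, so none is disputed here. It should be fixed, but it does not threaten the trial's main conclusion.

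**What to change.** Choose one of two edits to SAP 7.5, before unblinding.

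1. State that, within a dose and once UPDRS-III is significant, ADAS-Cog 11 and CIBIC+ are tested by Holm (or Hochberg) at an overall two-sided 0.05.
2. Delete the claim of an overall 5% level for that dose and describe the secondary p-values as unadjusted.

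In either case, correct the opening count to one primary and two secondary endpoints. Bring the protocol summary's single-secondary wording into line, or rely on SAP 7.3, which gives the SAP precedence.

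**Cost.** Option 2 costs no power. For option 1, given an open gate and the SAP 6 inputs (noncentralities 3 / (6 × √(2/80)) = 3.162 and 0.5 / (0.95 × √(2/80)) = 3.329; normal approximation, correlation 0 to 0.7):

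| Scenario | ADAS-Cog 11 power | CIBIC+ power |
|---|---|---|
| Both at planned effect (3 and 0.5 points) | 88.5% to between 86.6% and 87.7% | 91.5% to between 89.0% and 90.5% |
| Smaller effects (2.0 and 0.3 points) | 56% to 49% | 51% to 45% |
| Only that endpoint has its planned effect | 88.5% to about 82% | 91.5% to about 86% |

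The text change is a sentence or two in SAP 7.5, plus the wording alignment in the protocol summary if that is amended.

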## 7.6. Baseline Definition

Baseline or pre-dose assessment is the last available assessment prior to time of first dose of double-blind treatment, unless otherwise specified. If there are multiple assessments collected on the same date, the average of these assessments will be used.

## 7.7. Derived and Transformed Data

The following definitions will be used.

### Baseline Age

Age (in years) will be determined at the baseline visit (V3) using the date of the baseline visit as recorded in the CRF.

### Study Day

Study day for the assessment date of interest should be calculated relative to the first dose date of double-blind investigational product using the appropriate formula below:

- If the assessment date of interest is on or after the first dose date of double-blind investigational product:
  - Study day = assessment date – first dose date of double-blind investigational product + 1
- If the assessment date of interest is before the first dose date of double-blind investigational product:

- Study day = assessment date – first dose date of double-blind investigational product

### 7.7.1. Handling of Incomplete Dates

Where necessary for the calculation of derived variables, partial dates will be completed using the earliest calendar date based on the partial date provided. This rule is valid for all partial dates with the exception of the following:

- Start and stop dates of adverse events
- Start and stop dates of concomitant medication
- Start and stop dates of double-blinded medication

Imputation rules for start and stop dates for the above 3 categories are described in Section 7.7.3.

Completely missing dates will not be replaced and the corresponding derived variables will be set to missing.

Note that for missing DLB diagnosis date, if the month is missing, January will be imputed. If the day is missing, the 1st of the month will be imputed. Thus, if a patient has only a year of diagnosis, then the imputed diagnosis date will be January 1 of that year.

### 7.7.2. Visit Windows

Actual times will be used in the listings, individual concentration-time profiles, and in the calculation of PK parameters.

There are 4 study periods during this study:

- The **Screening Period** is defined as the period of time prior to the subject receiving the first dose of single-blind placebo run-in medication.
- The **Single-Blind (or Placebo) Run-In Period** is defined as the period from the first dose of single-blind run-in medication and ends on the last dose date of single-blind run-in medication. The assessments taken on the date of the first dose of randomized double-blind study medication will be assumed to have been completed before the first dose of double-blind study medication and will be slotted to this period.
- The **Double-Blind Treatment Period** starts on the date of first dose of randomized double-blind investigational product and ends on the last double-blind dose date +7 days. If the first dose of randomized investigational product is taken on the same day as the baseline assessments, it will be assumed that the baseline assessments were completed before the first dose of investigational product was taken.
- The **Post-Treatment Period**. For efficacy and health outcomes data, assessments are regarded as Follow-Up if the assessment occurred >7 days after the last dose date of randomized investigational product.

Data collected at assessment visits provide information of the status at that point in time (eg, efficacy measures, vital signs, laboratory parameters, etc.) and may provide biased results if the visit is attended early or late, in which case the subject will have received more or less treatment

than scheduled. For this reason, visits will be slotted with similar investigational product exposure.

Data will be phased first. All data that slots into the screening period will be assigned a visit of Screening. All data that occurs in Single-Blind Run-In Period will be assigned a visit of Run-in or Baseline depending on medication start/stop dates and data that slots into the Follow Up Period will be assigned a visit of Follow Up.

Post-baseline assessments from the Double-Blind Treatment Period data will be visit slotted according to the time intervals shown (Table 14) based on the days relative to the date of first dose of double blind investigational product (Day 1). Early withdrawal data that is assigned to Double-Blind Treatment Period will be slotted using the assessment windows.

Data will be assigned to analysis windows based on Table 14. This table defines the analysis windows associated with the screening, double-blind treatment period and follow-up periods of the study for assessments collected at each visit.

**Table 14: Windows of Relative Time Used to Classify Subject Assessments (Study RVT-101-2001)**

Period	Visit Number	Nominal Day	Actual Study Day 	
			Lowest	Highest
Screening (Week -6) 	1	-29		-1
Run-in (Week -2) 	2	-14	-39	-1
Baseline (Week 0)	3	1	1	1
On Treatment				
Week 1	4	7	2	10
Week 2	5	14	11	20
Week 4	6	28	21	35
Week 6	7	42	36	49
Week 8	8	56	50	63
Week 10	9	70	64	77
Week 12	10	84	78	105
Week 18	11	126	106	147
Week 24	12	168	148	last dose+7
Follow-up (Week 26)/ET	13	182	+7	

 Actual study day is derived by (visit date – run-in date) + 1 for Screening visit; (visit date – first dose date) + 1 for other visits except for Screening visit.

 Visit window for Screening visit is relative to run-in visit instead of Baseline visit.

 Visit windows may be adjusted to account for 2 10-day extensions to the run-in period allowed per protocol.

For data where two or more assessments are slotted into the same visit interval, the data recorded closest to the target visit day will be used for the summary tables and analyses. If two

assessments are equally close to the target day, the later of the two assessments will be used in tabulations and analyses; data from the earlier assessment(s) will be listed only.

- Note that for safety data analysis by visit (except blood pressure or heart rate assessments), the closest assessment is always the assessment used, however, for efficacy, if the closest assessment is not evaluable (or is missing), the other assessment would be used. For example, for ADAS-Cog, if the total score could not be calculated for the closest assessment, another assessment would be used. For “anytime” analysis of the safety data, all data points will be used.
- If on one of the dates only one blood pressure measurement is available (ie, only one of either the supine, sitting or standing measurements), then the assessments recorded on the other date, which slots to the same visit interval, will be used in tabulations and analyses. A similar rule applies for pulse rate assessments.
- Orthostatic blood pressure and heart rate will be calculated using vital sign measurements from whatever 2 body positions they are collected. If vital signs are collected in all 3 body positions (supine, sitting and standing), the supine and standing measurements will be used to calculate orthostatic blood pressure and heart rate.

For data where two or more assessments are slotted to follow up (and thus after double-blind treatment has ended), then the data recorded closest to target day (14 days after last dose of double-blind medication) will be used for summaries by visit. For the “anytime” analysis, all data points will be used.

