### 8.1. Time and Events

The Time and Events Schedule ([Table 2](#)) displays each study assessment and procedure along with the time of occurrence. All study assessments should be conducted by the investigator, and/or a suitably qualified designee approved and documented for this study. With the exception of the determination required in inclusion criterion #1, all study assessments and determinations may be delegated by the investigator to a suitably qualified designee approved and documented for this study. A qualified physician should be responsible for all study-related medical decisions and care. If the principal investigator is not a physician, he/she must delegate medical decisions and care to a qualified physician. All raters will be trained and certified to perform the specific rating scales in this study.

For Visit 3 there is a visit window of +5 days. For Visits 4 through 12, there is a visit window of  $\pm 5$  days (in relation to the Baseline visit). It is important that all visits should be scheduled relative to the Baseline visit, except for Visit 13. If the visit window is used, the subsequent visit should remain according to the planned visit schedule (i.e., the subsequent visit date should not be re-calculated from the date of the previous visit but should remain relative to Baseline).

Information will be recorded in the source documents and, where appropriate, the eCRF.

If, during the visit, the subject is unable or, in the judgment of the investigator, unlikely to be able to complete the cognitive assessments, the testing may be rescheduled within the windows described previously.

Subjects may be given breaks during the assessments or may have assessments split across different days so long as all assessments are completed within the visit window. Individual assessments or cognitive batteries such as the CDR computerized assessment system should, however, be completed within a single day.

Every effort should be made to administer the CDR computerized assessment system within  $\pm 1$  hour of the time of day of the Baseline administration on subsequent visits for each subject due to the potential for circadian fluctuation in scores. This should be taken into consideration when scheduling and performing Baseline CDR System assessments.

The order of rating scales should, when possible, be held constant, with the CDR computerized assessment system given to the subject first at each visit.

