The Single-Blind Run-In Period may be extended for 1 to 10 days for subjects who do not meet MMSE stability criterion for randomization at Visit 3. If, after the first extension to the Single-Blind Run-In Period, the subject still does not meet the MMSE stability criterion for randomization, the run-in period may again be extended for an additional 1 to 10 days. No more than 2 extensions to the Single-Blind Run-In Period will be allowed. No new IP will be dispensed for the extended run-in periods; subject should be instructed to continue taking blinded IP dispensed at Visit 2.

**Baseline (Visit 3) and Double-blind Treatment (Visit 4 through Visit 12):** At Visit 3 (Baseline), assessments will be performed to determine subject eligibility. Subjects who require one extension to the Run-in period will have a new Baseline visit occurring no more than 10

days after the originally intended Baseline at Visit 3. Subjects who require two extensions to the Run-in period will have a new Baseline visit occurring no more than 20 days after the originally intended Baseline at Visit 3.

Eligible subjects will be randomized to one of 3 groups, 35 mg RVT-101, 70 mg RVT-101, or placebo, for the 24 weeks of double-blind treatment assessment. At the Baseline visit, subjects will ingest the first dose of double-blind IP in the clinic in the presence of study center personnel (2 tablets; one from each bottle). Subjects will be instructed to take two tablets of IP once daily at bedtime, ***one tablet from each of 2 bottles***, beginning on the day after the Baseline visit.

At each visit, subjects will be reminded to take one tablet of blinded IP from each bottle once daily at bedtime. Compliance with IP should be assessed at all visits.

Throughout the Baseline and Double-Blind Treatment Periods, all clinic visits will be scheduled according to specified visit windows, and all specified assessments will be completed (Table 2). There will be weekly clinical assessments for the first two weeks of treatment, bi-weekly assessments until Week 12 and every six weeks thereafter. For Visits 5, 7 and 9, subjects may be given the option of whether to have assessments performed at the clinical study site or by a trained, visiting nurse in their own home.

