An independent Safety Monitoring Committee (SMC) will review interim safety data accumulated after approximately 30 subjects have completed 4 weeks of double-blind treatment and throughout the study at points specified in the SMC Charter. The SMC will provide their recommendation regarding the acceptability of reducing the visit frequency by omitting certain visits (Visits 5, 7 and 9) for both newly enrolled subjects and subjects active in the study at the time of the recommendation. Study enrollment will not be stopped or slowed to wait for SMC's recommendation and will proceed as planned with all visits until the SMC recommendation is made. Site will be formally notified of the SMC's recommendation regarding whether Visits 5, 7 and 9 can be omitted. [The meeting did occur and the SMC recommended Visits 5, 7, and 9 be omitted.]

After completion of Visit 12, the subject may be considered for enrollment in the extension study RVT-101-2002. If the subject does not enter the extension study, he/she will return for the Safety Follow-up Visit (Visit 13). Subjects who enter the extension study will not be required to complete Visit 13.

A study schema is shown in [Figure 1](#) and study scheduled assessments are presented in [Table 2](#).

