#### **9.3.1.1. Further Details of the MMRM Analysis**

The mixed model for repeated measures (MMRM) model will be fitted using SAS PROC MIXED procedure with restricted maximum likelihood estimation, an unstructured covariance matrix, and the Kenward-Roger approximation for denominator degrees of freedom. The unstructured covariance is the least restrictive and generally performs well with limited number of repeated measures per patient and puts no parameters on the data with respect to the covariance structure assumptions.

- Only in the unlikely circumstance that there are convergence problems with the MMRM analysis will other covariance structures be examined to resolve the convergence issue, ie, we would evaluate other additional variance-covariance structures, including compound symmetry (CS), heterogeneous compound symmetry (CSH), and auto-regressive [AR(1)]. In this eventuality, the Akaike’s Information Criterion (AIC) will be used to determine the optimal variance-covariance structure matrix for the primary comparisons.
  - If convergence issues arise, the base by visit interaction may be dropped.

*Sample* SAS code is as follows. The actual SAS code may be modified as appropriate. Note that the treat\*region interaction will be assessed for significance (at alpha 0.10), and if not significant, will be dropped from the model.

```
ods trace on;
```

```
Proc mixed data=MMRM1 method=reml PLOTS (MAXPOINTS=200000000000);
  class usubjid trt avisitn region;
  model chg=trt avisitn trt*avisitn trt*region base basemmsescore
base*avisitn region /ddfm=kr;
  repeated avisitn/subject=usubjid type=un r;
  lsmeans trt*avisitn/pdiff cl ;
  lsmeans trt*region/pdiff alpha =0.10;
  ods output lsmeans=_LS diffs=_lsdiff tests3 =tst;
run;
ods trace off;
```

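### SAP Table 14 ends Week 1 on study Day 10, but the schedule allows Visit 4 up to study Day 13, so compliant Visit 4 data on Days 11–13 are labelled Week 2, where UPDRS-III, ECG, C-SSRS and physical examination are not scheduled

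*SAP*

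**What the plan says.** - **Visit tolerance.** Protocol 8.1: "For Visits 4 through 12, there is a visit window of" ±5 days, counted from Baseline. Both Time and Events tables put Visit 4 at day 7 ± 5, with Baseline as day 0.
- **Day count.** Protocol 8.1: "At the Baseline visit, subjects will ingest the first dose of double-blind IP in the clinic". SAP 7.7, Study Day: "Study day = assessment date – first dose date of double-blind investigational product + 1". The Baseline date is therefore SAP Day 1. SAP 7.7.2 uses the same origin for slotting.
- **Windows.** SAP Table 14 ("Windows of Relative Time Used to Classify Subject Assessments") gives Week 1 nominal day 7 and Days 2–10. The next row reads "Week 2 5 14 11 20": Visit 5, nominal day 14, Days 11–20. Slotting is by study day. There is no window specific to a scale and no rule that falls back on the nominal visit.
- **What is scheduled.** Both Time and Events tables mark UPDRS-III, ECG, C-SSRS and physical examination at Visit 4 and not at Visit 5. Vital signs and the orthostasis questionnaire are marked at both. SAP section 3 records that "the SMC recommended Visits 5, 7, and 9 be omitted".
- **Model.** SAP 9.3.1.1 fits visit as a class effect with an unstructured covariance and Kenward-Roger degrees of freedom. Only if convergence fails "will other covariance structures be examined to resolve the convergence issue"; the baseline-by-visit term may then also be dropped.
- **Conflicting text.** SAP 9.3.2 says the primary endpoint was collected only at baseline, Week 4 and Week 24. The imputation steps in 9.3.4.3 name the same two post-baseline visits.

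**The concern.** A subject who attends Visit 4 within the allowed tolerance can have the data filed under a different visit. For UPDRS-III that visit does not exist. Each subject has one Visit 4 rating, so a compliant subject contributes to Week 1 or to Week 2 and never to both. The primary MMRM would then carry a visit level that nobody planned, and an unstructured matrix would contain a Week 1–Week 2 covariance that no subject informs. The stakes are the stability of the primary model fit, because a failed fit leads to a different covariance structure, and the completeness of Week 1 rows in by-visit efficacy and safety tables.

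**Working it through.** **1. Reproducing Table 14's cuts.** The upper bounds are midpoints of adjacent nominal days. Week 1/Week 2: (7 + 14)/2 = 10.5, giving 10 as stated. The later bounds 35, 49, 63, 77, 105 and 147 reproduce exactly, for example (28 + 42)/2 = 35. Week 2 gives (14 + 28)/2 = 21 against a stated 20, a one-day difference of no consequence here.

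**2. Permitted days against windows.** SAP study day = protocol day + 1, and permitted protocol days are nominal ± 5.

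| Visit | Permitted SAP days | Table 14 window | Permitted days outside |
|---|---|---|---|
| V4 (Week 1) | 3–13 | 2–10 | 11, 12, 13 |
| V5 (Week 2) | 10–20 | 11–20 | 10 |
| V6 (Week 4) | 24–34 | 21–35 | none |
| V7 (Week 6) | 38–48 | 36–49 | none |
| V8 (Week 8) | 52–62 | 50–63 | none |
| V9 (Week 10) | 66–76 | 64–77 | none |
| V10 (Week 12) | 80–90 | 78–105 | none |
| V11 (Week 18) | 122–132 | 106–147 | none |
| V12 (Week 24) | 164–174 | 148 to last dose + 7 | none |

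For Visit 4, 3/11 = 27% of permitted days are misfiled. Table 14's nominal days use the day-0 count while its windows count from Day 1. Without the one-day shift, Days 11 and 12 would still fall outside.

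**3. Share of Visit 4 ratings affected.** The documents give no distribution of visit dates, so these are assumptions.
- Uniform over the 11 days: 3/11 = 27%, and 80 × 3/11 ≈ 22 per arm.
- Normal around SAP Day 8 with SD s, truncated to Days 3–13: share = [Φ(5.5/s) − Φ(2.5/s)] / [Φ(5.5/s) − Φ(−5.5/s)]. For s = 1.5 this is 4.8% (about 4 of 80 per arm). For s = 3 it is 18.1% (about 14 of 80).

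**4. Effect on the primary model.** If no subject has both a Week 1 and a Week 2 rating, the covariance between those levels never enters the observed-data likelihood. It is unidentified, not merely imprecise. In a numerical check with illustrative variances, 80 per arm and 10% late Visit 4s, moving that covariance from −10 to +20 left the REML criterion unchanged. Kenward-Roger uses the covariance matrix of the variance parameters, so a flat direction is a plausible source of a non-positive-definite Hessian or non-convergence.

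For the Week 24 contrast, 12 simulated REML fits were run assuming 80 per arm, SD 7.5, correlations 0.45–0.6, 15% missing at Week 24 and 15% of Visit 4 ratings misfiled. The 70 mg estimate moved by at most 0.07 points against a standard error of about 1.3, and the standard error was essentially unchanged. These fits used neither PROC MIXED nor Kenward-Roger, so they do not settle whether the planned code would converge.

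**5. What a scale-specific midpoint gives.** UPDRS-III is scheduled at nominal days 7, 28 and 168. (7 + 28)/2 = 17.5, so Week 1 = Days 2–17 and Week 4 starts on Day 18. All permitted Visit 4 days (3–13) and Visit 6 days (24–34) then fall in the right slot: 0 of 11 misfiled instead of 3 of 11.

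**The case against.** The windows are meant to group data by similar drug exposure, not to mirror visit tolerance, and the Day 10/11 cut is simply the midpoint. The permitted Visit 4 and Visit 5 days overlap on Days 10–13, so no single cut could hold both while Visit 5 existed, and subjects seen before the committee's recommendation may have Visit 5 data that need a Week 2 window. That stands for vital signs and the orthostasis questionnaire. It does not justify a Week 2 slot for scales never scheduled there. If Week 2 is instead read as not applying to those scales, Days 11–20 have no slot and valid ratings drop out.

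SAP 9.3.2 and 9.3.4.3 imply that there is no Week 1 UPDRS-III at all. If they govern, the MMRM consequence disappears and only the labelling of other Visit 4 data remains. Both schedules carry the Visit 4 mark, so this is an unresolved conflict between passages.

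A reader might infer that the primary result is biased, that the model will fail, or that safety data are lost. The documents support none of these. Every permitted Visit 12 day lies in the Week 24 window, and a covariance that no subject informs does not itself bias Week 24. Failure is possible but not shown, and a fallback is prespecified. The any-time safety analyses use all data points, and vital signs were scheduled at Visit 5, so a late Visit 4 reading does not land where that measure is absent.

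**Conclusion.** Table 14 is wrong as written for Visit 4, with low-to-moderate impact. That 3 of 11 permitted days are misfiled follows directly from the documents. Week 24 values are not moved. Two effects remain: a depleted Week 1 level in by-visit tables and, conditional on UPDRS-III being rated at Visit 4, a sparse Week 2 level in the primary MMRM with an unidentified covariance that can trigger the fallback structures. The number of subjects affected is unknown; about 5% to 27% of Visit 4 ratings (roughly 4 to 22 per arm of 80) rests on assumed visit-date distributions.

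**What to change.** Before unblinding:

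1. For assessments not scheduled at Visits 5, 7 and 9, define scale-specific windows by the midpoint rule between visits at which that scale is scheduled. For UPDRS-III, Week 1 = Days 2–17 and Week 4 starts on Day 18. Assign every later day explicitly so that none lacks a slot. For UPDRS-III the next midpoint is (28 + 168)/2 = 98, which would lower the start of Week 24 from Day 148 to Day 99. No scheduled rating falls between, but an off-schedule or withdrawal rating could, so that choice should be deliberate and written down.
2. Keep the existing Week 2, 6 and 10 windows for assessments that were scheduled at those visits, such as vital signs and the orthostasis questionnaire. A wider Week 1 window applied to everything would pull Visit 5 data into Week 1, and deleting the Week 6 and 10 windows outright would leave Days 36–49 and 64–77 unassigned.
3. State that MMRM visit levels are only those at which the scale is scheduled.
4. Reconcile the Visit 4 UPDRS-III mark in both schedules with SAP 9.3.2 and 9.3.4.3.

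The cost is a small amount of extra programming to carry more than one set of windows.
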